Splanchnic nerve block			X (CS)					
Phone Call						X (CS)	X (CS)	X (CS)

\*Phone call will capture mortality status and number of subject admissions to the hospital since procedure

Following enrollment into the study the subject will undergo the following tests/measurements. A majority of the clinical testing occurs as part of the clinical study (CS) however the main procedure of RHC is standard of care (SOC).

Pre-procedure: Following information will be collected from the subject's charts that will be done as standard of care (SOC). Study specific tests/recordings are also listed below:

- If the subject is female and childbearing potential and has not had a pregnancy test since the arrival to the hospital, a blood pregnancy test will be done (CS). If positive the subject will be excluded from the study.
- Subjects will have strict measurement of urine output (SOC). A urine sample will be sent to the laboratory to check for the sodium concentration (CS). Subjects requiring a foley catheter will have measurements taken at comparable time intervals (SOC).
- Recorded vitals including weight, BP, HR, RR, SPO2 on the day before procedure and within 1h before procedure (SOC) and record heart rate variability using a non-invasive wrist monitor for 5 minutes (CS).
- Orthostatic vitals (5 minutes supine, 1+5 minutes sitting and 1+5 minutes standing) on the day before procedure and within 1h before procedure (CS). Also we will document whether s has symptoms bending over for 10 seconds (bendopnea).
- Labs: Basic metabolic panel (BMP) (SOC), brain natriuretic peptide (BNP) (CS), urine sodium (CS) plasma angiotensin II (CS), plasma arginine vasopressin (CS), plasma catecholamines. This will not require an extra lab draw. Total expected blood loss is <20ml.
- Dyspnea questionnaire using a 7-point Likert scale and Visual Analog Scale (CS)
- Six minute walk test (CS)
- Echocardiogram at baseline and after the block will be performed while the subject is on the cath table (CS). This is considered one continuous echo. This ultrasound test will also be used to look at liver blood flow.
- If the subject is on diuretics medications the scheduling of the medication will be adjusted to minimize interference with the study intervention.

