  - The subject will be asked to hold the morning diuretic medication and the morning dose will be given 3 hours after the procedure (CS). This is not expected to provide any risk to the stable chronic heart failure subject, especially since the diuretic medication will be resumed after completion of study that same day.
- Other medications can be continued, unless otherwise specified in the exclusion criteria.

Procedure:

1. Subjects will undergo elective right heart catheterization in the Duke catheterization laboratory lab as ordered by the primary team. A

cardiopulmonary exercise test will be added if not already ordered by the primary provider. Central hemodynamics will be recorded (baseline, prior to nerve block) (SOC). The access site for the right heart catheterization will be radial, brachial or cervical (SOC) to allow a prone positioning of the subject for the splanchnic nerve block described in the next paragraph. Additional baseline RHC numbers will be recorded with legs elevated, which is done to simulate a fluid bolus.

If the subject's hemodynamics provide any other concern for complications related to the splanchnic nerve block (such as underfilling or severe pulmonary hypertension, not related to left heart failure) as determined by the study personnel, the splanchnic nerve block and associated monitoring will not be performed. The subject will be considered a screen failure. Any information and samples collected prior to this will be discarded/destroyed per institutional policies.

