## 7. Selection of Subjects:

Subjects will be recruited from Duke University Medical Center outpatient environment. All potential study subjects will be scheduled electively by the cardiologist for a RHC +/- an invasive cardiopulmonary exercise. Subjects will be identified via a routine screen of the outpatient cath schedule weeks ahead of time.

The study will enroll subjects who meet the criteria as detailed below. Potentially eligible subjects will be contacted and informed about the possibility of the study. The actual consent process will occur on the morning of the procedure. The primary enrollment target is up to 30 subjects (15 HF with preserved ejection fraction and 15 HF with reduced ejection fraction).

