### **9. Consent Process**

Candidate subjects will be informed of the risks and benefits of participation in the study. They will be informed of the study process and demands. They will be given a copy of the informed consent document to review and afforded adequate time to do so.

Informed consent will be obtained prior to the right heart catheterization. Consent will be obtained by Study PI, Duke Heart Center study coordinators who are trained on the study and who have been trained on Informed Consent Process and other key personnel as designated by the PI. Consent will be obtained in the catheterization laboratory holding area. A subject is considered enrolled in this clinical study at the time at which the subject and investigator or authorized designee have personally signed and dated the Informed Consent Form.

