### **15. Data & Safety Monitoring:**

Due to the experimental nature of this intervention, data will be recorded after each subject completes the intervention for signs of unintended negative effects. These include hypotension, worsening renal function, or clinical deterioration. Additionally, subject's electronic medical data will be screened for any traumatic complications from the nerve block at 48 hours post-procedure.

Unanticipated adverse events, which are severe (listed above), will be reported to the IRB within 24 hours. Any other adverse event will be reported to IRB within 10 working days or per IRB policy. The Principal Investigator will also provide an annual report of any side effects or problems to the IRB during the study renewal process.

Following discharge, the subject's medical record will be monitored for readmission to the Duke hospital for heart failure for 6 months.

No PHI is sent outside of Duke.

16. **Privacy, Data Storage & Confidentiality** – see Section 12 of the e-IRB submission form and complete the questions in that section.

1. Data will be obtained by approved study personnel. An enrollment log will also be maintained in Excel Spreadsheet on the Heart Center's S:drive. The subject ID will also be stored on the folder to track subject enrollment and collection of data. Data will be recorded in Excel. Only deidentified data will be available for statistical analysis. All subject identifiers will be removed for database storage, statistical analysis and data reporting. This data will be stored on a study specific folder on the Duke server behind the Duke firewall. The subject ID code will be destroyed after data analysis is completed. Protected health information will not be used for any other purposes than those described in this protocol without obtaining further IRB approval. This information will be used for research purposes only and subjects will never be contacted regarding information obtained through chart review. A designated statistician from the DCRI will provide support with statistical analysis.

The adequacy of the Research Data Security Plan (RDSP) will be evaluated and approved by the Cardiology CRU prior to study conduct.

Any publications or presentations that result from this research will not identify any subjects individually, and will present data in aggregate form only.

Gathered data will be stored for at least 6 years.

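### The plan destroys all information on consented subjects whose block is withheld on hemodynamic grounds, so the trial dataset has no assured record of their pre-block adverse events or of why they were stopped

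*Combined protocol and SAP*

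**What the plan says.** **Consent and enrollment (Section 9).** "Informed consent will be obtained prior to the right heart catheterization". Enrollment is then defined by signature of the consent form: "A subject is considered enrolled in this clinical study at the time at which the subject and investigator or authorized designee have personally signed".

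**Study procedures before the block (Section 4).** "Following enrollment into the study the subject will undergo the following tests/measurements". The pre-procedure list includes tests marked as belonging to the clinical study: orthostatic vitals, a six-minute walk and several laboratory tests. The morning diuretic is held, also for the study. An exercise test is added where the provider has not already ordered one.

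**The stop (Section 4, Procedure, step 1).** If the hemodynamics raise a concern about complications of the block (the examples are underfilling and severe pulmonary hypertension not due to left heart failure), then "as determined by the study personnel, the splanchnic nerve block and associated monitoring will not be performed". The plan goes on to classify such a person: "The subject will be considered a screen failure". The next sentence is "Any information and samples collected prior to this will be discarded/destroyed per institutional policies".

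**Numeric limits (Section 7, Exclusion criteria, Procedure).** Subjects are also excluded on wedge pressure, with limits of 15 mmHg at rest and 25 mmHg at peak stress (12 and 22 on inotropes). The same item names study-personnel judgement of risk. It does not mention destruction of data.

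**Retention, safety and target.** Section 16: "Gathered data will be stored for at least 6 years". Section 15 ties the recording of unintended effects to completion of the intervention by each subject and separately requires adverse events to be reported to the IRB. Section 16 also provides for an enrollment log. Section 7: "The primary enrollment target is up to 30 subjects", 15 in each ejection-fraction group.

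**The concern.** A screen failure is usually someone turned away before research procedures begin. Here the label is applied to people who have consented, are enrolled by the plan's own definition, and have been exposed to research procedures. Destroying their information has three consequences.

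- **Safety.** An adverse event during the walk test, the diuretic hold, the study blood draws or a study-added exercise test has no assured place in the trial dataset. The routine safety recording in Section 15 does not catch it either, because it follows completion of an intervention that these subjects never receive.
- **Selection.** Section 4 (Efficacy endpoints) lists wedge pressure, during exercise and at rest, among the primary endpoints. Section 7 selects on wedge pressure, and underfilling is one of the examples given for the judgement stop. In an uncontrolled before-and-after comparison, a reader needs to know how many were stopped, at what pressures and on what ground.
- **Counting.** The same subject is enrolled under Section 9 and a screen failure under Section 4. It is therefore unclear whether that subject fills one of the 15 + 15 places.

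**Working it through.** The plan gives no figure on this point, so the check is mainly a comparison of its sections.

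**1. Order of events.** Consent and enrollment (Section 9) come first, then study-specific tests with the diuretic held (Section 4, Pre-procedure), then resting and leg-raise catheter readings (Section 4, Procedure, step 1). The judgement stop and destruction order come next in the text. The Valsalva maneuver and exercise are described after them. A stop at the place where it is written therefore comes after research procedures but before exercise. The Section 7 rule uses a peak-stress wedge, so an exclusion that depends on that value can only follow exercise.

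**2. Destruction against retention.** Section 4 covers any information collected before the stop and lists no exception. Section 16 keeps gathered data for at least six years and also lists no exception. For a stopped subject both cannot be followed as written.

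**3. What may survive.**
- Adverse-event reports to the IRB (Section 15), which are not limited to blocked subjects.
- The clinical chart, since the catheterization is standard of care.
- The enrollment log (Section 16), although no field for the stop or its reason is specified.

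No section asks for a count or description of stopped subjects.

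**4. Why the selection record matters (illustration on assumed values).** Let true resting wedge be normal with mean μ and between-subject SD 7 mmHg, let the within-subject SD be w, and keep subjects with measured resting wedge of at least 15 mmHg. Write s = √(7² + w²) and z = (15 − μ)/s. With no treatment effect, the expected change in those kept is −(w²/s) × φ(z)/[1 − Φ(z)].

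- μ = 20, w = 2: s = 7.28, z = −0.69, change about −0.2 mmHg, about 25% excluded.
- μ = 16, w = 4: s = 8.06, z = −0.12, change about −1.4 mmHg, about 45% excluded.

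Only 15 mmHg comes from the plan. The rest is assumed, and the peak-stress limit is ignored.

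**5. How many subjects (illustration).** Let g be the share of consented subjects who are stopped. The plan gives no rate, so 10% to 50% is assumed. If the target counts consents, the number blocked is 30 × (1 − g). If it counts blocked subjects, the consents needed are 30/(1 − g), rounded up.

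| g | Blocked, of 30 consented | Consents for 30 blocked |
|---|---|---|
| 10% | 27 | 34 |
| 20% | 24 | 38 |
| 30% | 21 | 43 |
| 40% | 18 | 50 |
| 50% | 15 | 60 |

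Records destroyed: 3 to 15 under the first count, 4 to 30 under the second. The number blocked falls below the 16 used in Section 14 only if g exceeds 1 − 16/30 = 46.7%.

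**The case against.** The strongest reply has four parts.

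- **Scope.** The destruction sentence belongs to a judgement stop written before the exercise step. The peak-wedge rule in Section 7 orders no destruction. This is correct. A reader might infer that every stopped subject has completed a maximal exercise test added for the study, but the documents do not support that. Some stops precede exercise, and some exercise tests will have been ordered clinically. Whether destruction also applies to the numeric exclusions is left open.
- **Surviving records.** IRB reports, the chart and the log remain, and destruction follows institutional policies that may limit it. So a reader should not infer that all trace of adverse events is lost or that the selection could never be examined. What stands is that the research dataset has no stated exception.
- **A specific rule over a general one.** The screen-failure sentence could be read as a deliberate privacy exception to six-year retention. That is possible, but the plan does not say so, and the subjects concerned are enrolled by its own definition.
- **The target is a ceiling.** It is worded as a maximum, and a screen failure may be meant not to fill a place. This also stands, and the remaining issue is the conflict between two definitions.

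**Conclusion.** The point holds and should be corrected before the trial relies on this rule. As written, it removes the research record of people already exposed to study procedures, and of how subjects were selected on a variable that is also a primary endpoint. The size is unknown because the plan gives no stop rate. The 3 to 15 of 30 consented subjects rests on an assumed 10% to 50%.

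Three stronger readings are not supported.

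- A reader might compare zero-event upper confidence bounds at 30 subjects with those at the smaller number blocked, and blame the difference on destruction. The safety endpoints listed in Section 4 are complications of the block. Subjects who never received it do not belong in that denominator, and keeping their records would not tighten the bound.
- A reader might infer that the destroyed values would yield an estimate of regression to the mean. They would describe the selection, but such an estimate also needs within-subject variability, which one baseline reading per subject does not give.
- A reader might infer a loss of power. No power or sample-size figure changes, and the number blocked stays at or above 16 unless more than 46.7% of 30 consented subjects are stopped.

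The selection occurs on baseline values before the block, not on post-treatment data.

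**What to change.** Replace the destruction sentence in Section 4 with a rule that a minimal de-identified record is kept for every consented subject:

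- study procedures begun;
- adverse events;
- rest pressures, and peak pressures if measured;
- whether the stop was by numeric limit or by personnel judgement.

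Stored samples may still be discarded.

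Then:

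- report the flow from consent to block;
- report adverse events of pre-block study procedures in all who began one, and block safety and efficacy in those blocked;
- reconcile screen failure in Section 4 with enrolled in Section 9, and the Section 4 rule with the retention rule in Section 16;
- state whether the target of up to 30 (15 + 15) in Section 7 counts consented or blocked subjects.

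The cost is protocol and consent wording plus a few database rows. If the target is set on blocked subjects, more consents will be needed. No clinical rule has to change.

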#### **4. Design & Procedures:**

This study will be a prospective, uncontrolled clinical trial. The study will not be controlled as invasive monitoring of hemodynamics will be performed, allowing clear demonstration of a cause-effect relationship.

This study aims to piggy-back on an elective right heart catheterization (RHC) in subjects with chronic heart failure. The right heart catheterization will be part of the subject's standard of clinical care (SOC). Subjects eligible for this study will be referred to the Duke cath lab for the evaluation of cardiac filling pressures because it is found to be necessary by the outpatient provider. This will occur in the cardiac catheterization lab. Subjects get scheduled for RHC days to weeks (2-3) ahead of their procedure. The eligible subject will be contacted before the study to be informed about the eligibility for the study and basic information about the study will be provided over the phone shortly after they have been scheduled. Subject will be consented in person in the morning of the procedure.

The subject will undergo pre procedural testing as demonstrated below in the flow chart (all part of the clinical study - CS). Besides the RHC (SOC) the subject will undergo an invasive cardiopulmonary exercise with the RHC in place. Baseline evaluation is followed by a regional nerve block (bilateral splanchnic nerves) while the subject is in the catheterization lab. This will be performed by an anesthesiologist experienced in splanchnic nerve blocks.

Figure 2: Study flow chart

[figure not shown]

Table: Study events

Required Assessment	Pre procedure (day of)	Baseline (intra-procedure)	Block	Post Block Procedure	Recovery	24 h after procedure	48 h after procedure	6 Months after Procedure (±14 days)
Vitals (BP, HR, RR, SpO2)	X (SOC)	X (SOC)	X (SOC)	X (SOC)	X (SOC)			
Weight	X (SOC)				X (SOC)			
Orthostatic vitals	X (CS)				X (CS)			
Urine output (continuous recording)	X (CS)	X (CS)	X (CS)	X (CS)	X (CS)			
Valsalva		X (CS)		X (CS)				
Labs: BMP, pro-BNP, urine sodium,	X (SOC/CS)				X (CS)			
Labs (Angiotensin II), Plasma Metanephrines, Vasopressin, Plasma Catecholamines, Lactate		X (CS)		X (CS)				
Dyspnea Questionnaire		X (CS)		X (CS)	X (CS)	X (CS)	X (CS)	
Six minute walk test	X (CS)				X (CS)			
Impedance and lung fluid content measurement		X (CS)		X (CS)				
Heart rate variability	X (CS)	X (CS)	X (CS)	X (CS)	X (CS)			
Echocardiogram		X (CS)		X (CS)				
Invasive CPX		X (SOC/CS)		X (CS)				

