2. Unilateral splanchnic nerve block performed by an anesthesiologist (see images below) (CS). The anesthesiologist will perform a unilateral block to the splanchnic nerve. The blood pressure will be checked, after 15 minutes, post-block. If the systolic blood pressure is reduced by  $> 20$ mmHg, the contralateral splanchnic nerve will not be blocked. Following the right heart catheterization procedure the subject will be prone on the abdomen. Central venous access remains in place. Needle will be placed under fluoroscopic guidance in the posterior chest wall. Anesthetic solution (1.5% lidocaine with 1:200,000 epinephrine and of 0.5% ropivacaine) will be injected. Lidocaine 1.5% with Epinephrine 1:200,000 will be used initially to confirm extravascular administration. The subject will then be placed back on his/her back. The subject will then undergo repeat hemodynamic measurement with the RHC catheter that was already in place. Then the subject proceeds with invasive cardiopulmonary testing after a 30 minute break. The central venous catheter will be removed after the hemodynamic monitoring/testing is completed in the catheterization laboratory.

Additional measurements include:

- Orthostatic vitals (CS).
- Dyspnea questionnaire (CS)
- Echocardiography and liver flow measurements (CS)

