### Inclusion criteria:

- Age 18-90
- Followed at DUMC for known or suspected diagnosis of HF (NYHA stage 1-3, Class C-D), including subjects on inotropic medication
- Systolic blood pressure (SBP) > 100 mmHg
- Planned for elective diagnostic right heart catheterization

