#### **HF medication regimen:**

- Initiation of HF medications (in the 48 hours preceding the study) such as beta blockers, ACEI, ARB, aldosterone receptor blockers, calcium channel blockers of any type, central sympatholytics like clonidine, moxonidine,
- **Recent acute MI or hemodynamic instability:**
  - Acute MI (STEMI or Type I NSTEMI) within 7 days?
  - Evidence of progressive cardiogenic shock within 48 hours
  - Repeat systolic blood pressure <90mmHg or >180mmHg

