### **Pregnancy**

#### **Procedure**

- Unable to tolerate procedure as determined by subject or investigator
- will be excluded if invasive hemodynamics on study date determine that the subject does not have elevated filling pressures at rest or stress. Following pressures/situations will exclude the subject: wedge pressure <15mmHg (<12mmHg on inotrope) at rest and <25mmHg with peak stress (<22 with inotropes) and greater than the central venous pressure or determined by study personnel to be at risk for nerve block related complications.

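### The rule for withholding the second-side block has no absolute systolic floor, so from a pre-block systolic of 101 to 109 mmHg it still permits that block below 90 mmHg

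*Combined protocol and SAP*

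**What the plan says.** The planned intervention is a "regional nerve block (bilateral splanchnic nerves"), as section 4 (Design & Procedures) puts it. Step 2 of the procedure stages it: one side is blocked, pressure is checked 15 minutes later, and if systolic has dropped by more than 20 "mmHg, the contralateral splanchnic nerve will not be blocked". No absolute pressure enters that decision, and step 2 does not name the reading from which the drop is counted.

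Two systolic limits appear in section 7, both for eligibility. The inclusion criteria require "Systolic blood pressure (SBP) > 100 mmHg". The exclusion criteria, under recent MI or hemodynamic instability, list "Repeat systolic blood pressure <90mmHg or >180mmHg".

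Other provisions bear on hypotension around the block:

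- The study events table in section 4 schedules vitals, including blood pressure, in the Block column. Step 1 of the procedure adds telemetry and continuous non-invasive hemodynamic devices.
- Step 1 also says that if the hemodynamics raise concern, "the splanchnic nerve block and associated monitoring will not be performed". This is a decision taken before the block.
- The exclusion criteria under Procedure give two grounds that rest on judgement: "Unable to tolerate procedure as determined by subject or investigator" and "determined by study personnel to be at risk for nerve block related complications".
- Orthostatic vitals after the block, overnight observation if needed (Safety endpoints) and the review after each subject (section 15) come after the second-side decision.

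**The concern.** A rule based only on the size of a fall treats a drop from 140 to 120 mmHg and a drop from 101 to 81 mmHg alike: both are falls of 20 mmHg, neither exceeds 20, and the second side may proceed. For subjects who enter near the lower limit, following the rule exactly permits more sympathetic block at a systolic which, if confirmed on a repeat reading, would have kept the same subject out of the trial.

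The direction of risk is known. Section 3 names transient orthostatic hypotension as the most common side effect of this block and says that aggressive hydration beforehand typically prevents it; the protocol describes no such hydration here. The block is estimated to last 12 to 24 hours, and the subject goes on to a second invasive exercise test and a six-minute walk. Subjects on inotropes are eligible. The use in chronic heart failure is new, and section 12 says that unexpected side effects cannot be excluded.

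**Working it through.** The plan gives no figure of its own here, so there is nothing to reproduce. The check is direct arithmetic in whole mmHg.

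**Inputs**

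- Stop rule (section 4, Procedure, step 2): the second side is withheld if the fall F is greater than 20. A fall of exactly 20 does not meet the rule.
- Entry limit (section 7, Inclusion criteria): systolic above 100, so the lowest whole-number value is 101.
- Comparison value (section 7, Exclusion criteria): 90, there applied to repeat readings for eligibility.

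**Formulas**, with R the pre-block systolic:

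- Lowest systolic at which the second block is still permitted = R − 20.
- A fall that is permitted but ends below 90 needs R − F ≤ 89 and F ≤ 20, so F runs from R − 89 to 20.
- With an added floor of 90, the largest permitted fall is the smaller of 20 and R − 90.

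| R | Lowest permitted now (R − 20) | Permitted falls ending below 90 | Largest permitted fall with a floor of 90 |
|---|---|---|---|
| 101 | 81 | 12 to 20 | 11 |
| 105 | 85 | 16 to 20 | 15 |
| 109 | 89 | 20 only | 19 |
| 110 | 90 | none | 20 |

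The gap therefore covers R from 101 to 109, with a shortfall below 90 of at most 9 mmHg (from 101) and at least 1 mmHg (from 109). At 110 a result below 90 needs a fall of at least 21, which already meets the stop rule.

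**Assumption range.** The table assumes that the pre-block reading still satisfies the entry limit. The protocol does not say that this limit is checked again immediately before the injection, and baseline exercise testing comes first. If R had drifted to 100, 95 or 90, the lowest permitted value would be 80, 75 or 70. The documents do not say whether this would occur.

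**Other provisions.** Vitals in the Block column and continuous recording would show a low value, but no systolic value is tied to an action. The two grounds that rest on judgement carry no number either. The fall of more than 20 mmHg is the only numeric criterion between the first side and the second.

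**The case against.** The strongest reply is that the gap is covered in practice. An experienced anesthesiologist performs the block with pressure monitored. Step 2 forbids a second block after a large fall and never requires one otherwise. The grounds for stopping that rest on judgement are not limited to the time before the first injection. All of this stands, and it is why the practical effect is probably small. It does not supply a floor: the protocol chose a number for this decision, and that number does not protect the subjects with the lowest starting pressure.

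A second reply is that 90 mmHg is borrowed. It is an eligibility limit on repeat readings, and a transient value on the table after a block expected to lower pressure is a different thing. This also stands. A reader might infer that the protocol contradicts itself; it does not, because nowhere does it offer 90 mmHg as a limit during the procedure. Nor does consistency with eligibility single out 90, since a subject at 90 to 100 mmHg would also fail the inclusion limit.

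Three further inferences go beyond the documents:

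- That every other hypotension safeguard acts only after the second-side decision. Blood pressure is scheduled during the block itself; what is missing is an action value.
- That subjects should be expected to reach 81 to 89 mmHg. These are the lowest permitted values, at a fall of exactly 20 mmHg. No distribution of starting pressure or of the fall after one side is given, so no probability can be attached.
- That the unnamed reference reading is a serious ambiguity. Section 4 provides several readings, from the day before to the intra-procedure baseline, but the natural meaning is the value just before the block. Naming it is a clarification.

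**Conclusion.** The point holds as a cheap improvement. Followed exactly, the rule permits the contralateral block at a systolic 1 to 9 mmHg below 90 after the largest non-triggering fall from a starting value of 101 to 109 mmHg, and has no such effect from 110 mmHg upward. This rests on the stop rule being strictly more than 20 mmHg and on the pre-block reading still being above 100 mmHg; a lower reading would widen the gap. It is a gap in a safety rule, not a contradiction between sections, and it does not bear on the planned statistical tests. How many of the up to 30 subjects would fall in the range is not stated; the number is probably small.

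**What to change.** Amend section 4, Procedure, step 2 so that it reads in substance: *the contralateral side is not blocked if, 15 minutes after the first block, systolic pressure has fallen by more than 20 mmHg from the reading taken immediately before the first injection, or is below 90 mmHg on a repeat reading.* The 90 mmHg is a proposal taken from the exclusion criteria, and it still allows a second block at 90 to 100 mmHg; the investigator and anesthesiologist may set a higher floor.

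The cost is one sentence, plus one repeat cuff reading when the 15-minute value is below 90 mmHg. The downside is that a few low-pressure subjects receive a one-sided block only, an outcome that step 2 already accepts. With a floor of 90 mmHg, nothing changes for subjects who start at 110 mmHg or more.
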